6.7 Treatment Arms

142 patients with ALS will be randomized in 2 parallel groups, in a ratio of 1:1. One group will be treated with RNS60 and one group will be treated with placebo.

Group A	RNS60 375 mL IV once a week + RNS60 4 mL inhaled once a day (six days/week) + Riluzole 50 mg twice a day
Group B	NS 375 mL IV once a week + NS 4 mL inhaled once a day (six days/week) + Riluzole 50 mg twice a day

6.8 Treatment Assignment and Subject Numbering

[...]

6.9 Concomitant Medications and Prohibited Treatment

Any concomitant treatment can be continued as per medical indication.

Except for other experimental drugs, there are no restrictions for concomitantly used medications. However, the subjects and investigators must keep records of the drugs on the concomitant medication section of the e-CRF along with daily dose and duration of use.

6.10 Study Drug Discontinuation

If study treatment is discontinued before the defined treatment duration period ends, the subject will be considered to have prematurely withdrawn from the study. Subjects lost to follow up should be recorded as such on the e-CRF. Subjects who discontinue study drug before completing the study should be scheduled for a visit as soon as possible, at which time all the assessments listed for the study completion visit will be performed for safety evaluations during the 30 days following the last dose of study drug. Subjects who discontinue the study drug should be considered withdrawn from the study after the final visit assessments are performed or when it is clear that the subject will not return for assessment.

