2.4 Secondary Endpoints

1. The mean change in the proportion of T-reg (measured via FOXP3 and CD25 mRNA); the mean change over time in the plasma concentrations of Cyp-A, 3-NT, Actin-NT, MCP-1, IL-17 during the follow up period (from 24 to 48 weeks);
2. The cumulative proportion of subjects becoming no longer self-sufficient at 4, 12, 24, 36 and 48 weeks in the two treatment arms (defined as those scoring 2 or lower on at least one of the ALSFRS-R items for swallowing, cutting food and handling utensils, or walking);
3. The mean change of ALSFRS-R total score in the two treatment arms during the treatment and follow up period;
4. The cumulative proportion of deaths or tracheostomies in the two treatment arms during the entire study including follow-up;
5. The mean change of FVC score in the two treatment arms during the treatment and follow up period;
6. The total number of subjects in the two treatment arms experiencing at least one AE leading to treatment discontinuation at 4, 12 and 24 weeks;
7. The mean number of AEs per treatment arm at 4, 12, 24 and 48 weeks;

8. The mean change of ALSAQ-40 score measuring quality of life at the completion of the treatment and follow up period.

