3 STUDY DESIGN

The study is a multicenter, randomized, double-blind, placebo-controlled, parallel group, add-on pilot trial in patients taking riluzole. Patients diagnosed with ALS who meet the study's inclusion and exclusion criteria and sign the Informed Consent Form (ICF) will be enrolled. There will be two groups making up a total of 142 subjects: Group A (71 subjects) and Group B (71 subjects). Subjects will be randomly assigned to receive treatment with either RNS60 or placebo while concomitantly taking riluzole (50 mg twice a day). RNS60 or placebo will be administered intravenously once a week as well as inhaled via nebulization every morning (6 days a week on non-infusion days) for 24 weeks. All visit windows (± 1 or $+ 4$ days according to study procedure) are consecutive calendar days and are calculated from the day the participant starts study treatment (the day of the Randomization-Baseline Visit).

Blood samples will be collected five times for enrolled subjects to measure biomarkers. The first blood sample collection will be at baseline before the first infusion dose. Safety and efficacy will be assessed by way of physical exam, vital signs and AEs. Changes in disability and quality of life will be assessed using the ALSFRS-R scale, FVC and ALSAQ-40 scale. The overall treatment duration will be 24 weeks. Each subject will be followed up for a maximum period of 48 weeks (24-week treatment + 24-week follow up) or until death or tracheotomy, whichever occurs first.

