6.11 Premature Subject Withdrawal

The duration of the study includes 24 weeks of treatment plus 24 weeks of follow up. Subjects may voluntarily withdraw from the study or can be dropped at the discretion of the investigator at any time. Subjects must be withdrawn from the study if any of the following occurs:

- Unwillingness to comply with procedures as outlined in the study protocol;
- Withdrawal of consent;
- Loss to follow-up;
- Repeated non-compliance to dosing regimen or visit schedule (intake of 50% of recommended dose or less in three consecutive intervals between visits);
- Intolerable adverse events which may or may not be related to study medication and, if deemed drug-related, non remitting with down titration;
- Death/Tracheostomy;
- Requirement of medication doses greater than those allowable in the study;
- Abnormal laboratory value(s) deemed of medical concern;
- Administrative problems;
- Female becoming pregnant;
- Severe protocol deviations (at the Study Coordinator judgment).

If a subject withdraws or fails to return for visits, the investigator must determine the primary reason for the subject's premature withdrawal from the study, and record this information on the study-completion visit. Subjects must return all unused/remaining study drug to the investigative site. For subjects who are lost to follow up, the investigator should show "due diligence" by documenting in the source documents the steps taken to contact the subject, e.g., dates of telephone calls, registered letters, etc. Subjects who are prematurely withdrawn from the study will not be replaced.

Discontinued use of riluzole during the treatment period implies the discontinuation of the experimental drug. The subject will undergo a final safety evaluation and data collected up to the time of drug discontinuation will be used in the data analysis.

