7.9 Study Duration

The overall duration of the study will be approximately 36 months as indicated below:

- Administrative and ethical procedures: 6 months
- Duration of subject enrolment: 12 months
- Study drug administration: 24 weeks/subject
- Follow-up period: 24 weeks/subject
- Close-out monitoring visits and statistical analysis: 4 months
- Final report and data publication: 2 months

Project's Gantt

[figure not shown]

Table 2. SCHEDULE OF PROCEDURES

		Treatment Period								Follow-up Period		End of study (only for drop outs)
		Randomization – baseline Day 1	Weeks 1 - 3	Week 4	Weeks 5 - 11	Week 12	Weeks 13-23	Week 24	Week 36	Week 48		
Screening (-28 days)	Screening (-28 days)											
Informed consent	x											
Patient's numbering assignment	x											
Date of visit	x	x	x	x	x	x	x	x	x	x	x	x
Demographic data	x											
Blood sample collection (biomarkers)		x		x		x		x		x		x
Personal and clinical data	x											
Physical exam	x	x										
Neurological exam	x	x		x		x		x	x	x	x	x
Medical history/ Concomitant medical disorders	x	x										
Concomitant medications	x	x	x	x	x	x	x	x	x	x	x	x
Inclusion/exclusion criteria	x	x*										
Randomization		x										
Study drug infusion		x	x	x	x	x	x					
Study drug management for nebulization		x	x	x	x	x	x	x				x
Study drug dispensing		x	x	x	x	x	x					
Vital signs, weight	x	x	x	x	x	x	x	x	x	x	x	x
Height	x	x										
ALSFRS-R scale	x	x		x		x		x	x	x	x	x
FVC	x	x		x		x		x	x	x	x	x
ALSAQ-40 scale		x						x		x		x

Clinical lab tests**	x	x		x		x		x		x		x
Pregnancy test		x						x				x
Compliance check (nebulization)			x	x	x	x	x	x				x
AE assessment		x	x	x	x	x	x	x	x	x	x	x
Reason of discontinuation												x

* Certain eligibility criteria are assessed at Day 1, prior to randomization

** According to the physician judgment. Clinical lab test needed for inclusion criteria could be valid if performed up to 6 months before randomization visit

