11 STATISTICS

11.1 Sample Size Calculation

We analyzed preliminary data on Cyp-A which showed an increase of 0.27 over six months (Nardo, G. et al. 2011). With 142 patients enrolled, we will have 80% power to detect a 44% decrease in the rate of progression in Cyp-A at a two sided $p=0.05$ significance level. This assumes a drop-out rate of 1.75% per month (10% over the study). The calculation is based on the method shown in (<http://hedwig.mgh.harvard.edu/biostatistics/node/42>). For the other biomarkers we only had data on the between patient variation and not on the within patient variation which could be used for calculating sample size for the proposed study. Usually the within patient variation is less than the between patient variation, so power calculated using the between patient variation is conservative. The T-reg values were assessed in slowly progressing vs. rapidly progressing ALS43 and the estimated difference was used as the difference expected to slow the progression of the disease in patients receiving RNS60. A total of 128 patients is needed to detect a difference in means of 0.25 units between the two treatment arms at 24 weeks with a standard deviation (SD) of 0.5. Similar assumptions were made for the other biomarkers for which, except for Actin-NT (that would require 1542 patients), numbers range from 8 to 68 (Nardo, G. et al. 2009; Nardo, G. et al. 2011; Henkel, J. et al. 2013; Chiò A. et al., 2011):

- MCP-1: a total of 16 patients is needed to detect a difference in means of 220 units between the two treatment arms at 24 weeks with a standard deviation (SD) of 140;
- Actin-NT: a total of 1542 patients is needed to detect a difference in means of 0.1 units between the two treatment arms at 24 weeks with a standard deviation (SD) of 0.7;
- 3-NT: a total of 24 patients is needed to detect a difference in means of 50 units between the two treatment arms at 24 weeks with a standard deviation (SD) of 40;
- Cyp-A: a total of 68 patients is needed to detect a difference in means of 1.4 units between the two treatment arms at 24 weeks with a standard deviation (SD) of 2.0.

For ALSFRS-R, the software <http://hedwig.mgh.harvard.edu/biostatistics/node/42> shows the variance parameters which are from the Celebrex Study.

The variance of the random effects is the matrix 31.8 (intercept), 0 .6687 (slope) with a covariance of 0.8527. The error has a variance of 2.7.

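### Stopping study drug before week 24 is treated as leaving the study, so the visible text does not collect death or tracheostomy status to week 48 for these subjects

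*Combined protocol and SAP*

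**What the plan says.** Section 6.10 gives the rule twice. The first statement is "If study treatment is discontinued before the defined treatment duration period ends, the subject will be considered to have prematurely withdrawn from the study". The second is "Subjects who discontinue the study drug should be considered withdrawn from the study after the final visit assessments are performed", or once it is clear that the subject will not come back. The final visit repeats the completion-visit assessments and is described as a safety evaluation in the 30 days after the last dose. Table 2 agrees: drop-outs have a single end-of-study column.

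Other sections widen the rule. Section 6.11 requires withdrawal from the study for, among other reasons, "Repeated non-compliance to dosing regimen or visit schedule". Section 11.3 adds two consecutive missed infusions, or low nebulizer use over three visits. A riluzole stop during treatment ends study drug (6.11) and so brings in 6.10.

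Against this, item 4 of section 2.4 is "The cumulative proportion of deaths or tracheostomies in the two treatment arms during the entire study including follow-up". Section 3 says: "Each subject will be followed up for a maximum period of 48 weeks (24-week treatment + 24-week follow up) or until death or tracheotomy". Section 11.2 uses a modified intention-to-treat population of everyone who took at least one dose, and analyses time to death or tracheostomy by Kaplan-Meier and log-rank. It gives no separate rule for subjects who stopped drug early. Section 11.1 assumes a drop-out of 1.75% per month, about 10% over the study.

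**The concern.** A patient who stops drug at week 6 belongs to the analysis population for a 48-week endpoint, but after the drop-out visit no visible text asks whether that patient is alive or has had a tracheostomy. In the survival analysis the patient would presumably be censored at that visit. Kaplan-Meier then relies on stopping being unrelated to prognosis. That is doubtful when the triggers include intolerable adverse events, abnormal laboratory values and missed weekly clinic infusions, any of which may accompany faster progression.

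Events will be few with 71 patients per arm. Section 11.2 lets a suggestive benefit (p<0.1) in the clinical measures and several biomarkers justify further study, so the clinical data feed that decision. Status not collected at the time may be hard to recover later.

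**Working it through.** **1. The plan's drop-out figure.** At 1.75% per month over 6 months, 1 − (1 − 0.0175)^6 = 10.05%, which reproduces the stated 10%. That figure therefore covers the treatment period only.

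**2. Patients affected (upper bound).** 24 weeks is 5.52 months: 1 − 0.9825^5.52 = 9.28%, and 0.0928 × 142 = 13.2. Counting 24 weeks as 6 months gives 0.1005 × 142 = 14.3. Both treat every drop-out as a drug stop.

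**3. Follow-up lost (upper bound).** A constant weekly hazard is λ = −ln(0.9825) × 5.52/24 = 0.00406. Patient-weeks lost = 142 × ∫ from 0 to 24 of λe^(−λt)(48 − t) dt = 477, out of 142 × 48 = 6,816 (7.0%).

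**4. Does other visible text fill the gap?** Section 9.5 follows adverse events already observed until they resolve. Section 9.4 says on which form a disease-related death or a tracheotomy is entered. Neither looks for new events in a withdrawn subject.

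**5. Effect on the survival results.** The documents give no death or tracheostomy rate, so the following is assumed: 48-week risk of 10 to 35%; a log-normal frailty (SD 0.5 to 1.5) that multiplies the event and stopping hazards alike; stopping in weeks 0 to 24 only; censoring at the stop; no true treatment effect; 71 per arm. With 9.3% stopping in each arm:

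- Log-rank-based hazard ratio: 1.00 (range over the grid 0.99 to 1.02).
- Events: at 25% risk and SD 1, 31.6 of 35.5 are observed, so about 4 are missed. Over the grid 8 to 21% of events are missed.
- Week-48 Kaplan-Meier risk, by frailty SD:

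| True risk | SD 0.5 | SD 1 | SD 1.5 |
|---|---|---|---|
| 10% | 9.8% | 9.2% | 8.5% |
| 25% | 24.6% | 23.6% | 23.0% |
| 35% | 34.5% | 33.6% | 33.1% |

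The Kaplan-Meier shortfall over the grid is 0.2 to 2.1 percentage points. If item 4 were reported as a crude proportion, the shortfall would be 0.8 to 3.5 points.

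**6. Sensitivity to the frailty link.** Step 5 assumes that one frailty drives both stopping and events. With a correlation of 0.5 between the two log-frailties, at 25% risk and SD 1, the Kaplan-Meier estimate is 24.3%. The shortfall halves, from 1.4 to 0.7 points.

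**The case against.** The strongest reply is that this is an absence claim about a document with text removed. Most of section 7 is not shown, including 7.6 on follow-up visits and 7.7 on the drop-out visit, and tracing may be described there. That stands, so the point is limited to the visible wording. But 6.10 says that the subject is withdrawn after the final visit, so any such tracing would conflict with it and 6.10 would still need correcting.

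A reader might infer that the rule contradicts section 3. It does not clearly do so: section 3 sets a maximum of 48 weeks, which allows shorter follow-up. The conflict is with item 4 of 2.4.

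A reader might also infer that the treatment comparison is biased. That needs stopping to be linked to prognosis and also to differ by arm. The placebo is saline on the same regimen, and the documents give no reason to expect a difference. Calculations with unequal stopping would be hypothetical and carry no weight here.

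The number affected may be well below 13. Section 6.11 lists death or tracheostomy among the reasons for withdrawal, so the plan's 10% may include them. At an assumed 25% 48-week risk and a constant hazard, 1 − 0.75^(24/48) = 13.4% would have the event by week 24, already more than 10%. Consent withdrawals and losses to follow-up reduce the number further. This also stands.

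Finally, 11.2 specifies Kaplan-Meier for survival, so the larger crude-proportion shortfall applies only if item 4 is reported literally as a crude proportion.

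**Conclusion.** The point holds as a cheap improvement of low to moderate priority. Followed as written, 6.10, 6.11 and 11.3 discard death and tracheostomy information that a secondary endpoint counts over the whole study in everyone dosed. The size is modest: at most about 13 to 14 of 142 patients, some events lost, and arm-specific Kaplan-Meier risk too low by at most about 2 points. That last figure rests on assumed event risks and an assumed full link between stopping and prognosis. With equal stopping no between-arm bias is expected.

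Two further inferences are not supported. One is that the primary 24-week biomarker analysis is undermined. It is a pharmacodynamic contrast fitted by maximum likelihood, with its missing-data condition stated in 11.2, and survival tracing does not bear on it. The other is that early stoppers must keep to the full visit schedule. That would bring off-drug samples into the pharmacodynamic contrast and could dilute it, which is a trade-off and not a plain gain.

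**What to change.** - **6.10, 6.11 and 11.3:** let a drug stop, a compliance trigger or a riluzole stop end study drug without ending study participation. Suggested wording: *Stopping study drug is not withdrawal from the study. Unless consent is withdrawn, death and tracheostomy status with dates (and ALSFRS-R if feasible) will be collected by telephone at weeks 36 and 48.*
- **11.2:** state that the survival analysis counts events to week 48 and censors only at consent withdrawal, loss to follow-up or week 48.
- **Biomarkers:** do not require post-discontinuation samples in the primary pharmacodynamic analysis.
- **7.6 and 7.7:** check that they agree with the amended text.

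The cost is one amendment with approval or notification at each institution (8.5), a CRF entry, and about 26 telephone calls (13.2 patients × 2 = 26.4) at the plan's drop-out rate. No sample size changes. The completer, complier and per-protocol populations in 11.2 still give the on-treatment view.

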6.11 Premature Subject Withdrawal

The duration of the study includes 24 weeks of treatment plus 24 weeks of follow up. Subjects may voluntarily withdraw from the study or can be dropped at the discretion of the investigator at any time. Subjects must be withdrawn from the study if any of the following occurs:

- Unwillingness to comply with procedures as outlined in the study protocol;
- Withdrawal of consent;
- Loss to follow-up;
- Repeated non-compliance to dosing regimen or visit schedule (intake of 50% of recommended dose or less in three consecutive intervals between visits);
- Intolerable adverse events which may or may not be related to study medication and, if deemed drug-related, non remitting with down titration;
- Death/Tracheostomy;
- Requirement of medication doses greater than those allowable in the study;
- Abnormal laboratory value(s) deemed of medical concern;
- Administrative problems;
- Female becoming pregnant;
- Severe protocol deviations (at the Study Coordinator judgment).

If a subject withdraws or fails to return for visits, the investigator must determine the primary reason for the subject's premature withdrawal from the study, and record this information on the study-completion visit. Subjects must return all unused/remaining study drug to the investigative site. For subjects who are lost to follow up, the investigator should show "due diligence" by documenting in the source documents the steps taken to contact the subject, e.g., dates of telephone calls, registered letters, etc. Subjects who are prematurely withdrawn from the study will not be replaced.

Discontinued use of riluzole during the treatment period implies the discontinuation of the experimental drug. The subject will undergo a final safety evaluation and data collected up to the time of drug discontinuation will be used in the data analysis.

6.12 Modification of Study Intervention/Investigational Product for a Subject

Any dosage adjustment, including the reason for and dates of adjustment, will be documented in the CRF for each subject requiring this manipulation. The PIs or licensed physician Sub-Investigator may reduce the dosage of study drug or discontinue the study drug in its entirety for AEs thought to be related to the study drug or for other reason during the trial (the reason for, and dates of

suspension or dose reduction must be documented). If the AE is mild or moderate, the dosage may be reduced until the event improves. The PIs may then choose to resume the higher dosage or maintain the subject at a reduced dosage. The option to continue with administration by IV only or inhalation only is allowable.

If the event is serious or life threatening, and deemed to be definitely drug related, the study drug will be discontinued immediately. Study subjects must remain off the study drug permanently. Subjects may not resume study drug. All AEs will be followed to resolution.

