5.1 Blood sample collection

Blood samples of a total volume of 21 ml will be collected from each subject five times during the entire trial. Fasting is not needed, but the patient is encouraged to have a light breakfast before blood collection. Blood for biomarker assessments will be collected in two 4-ml EDTA vacutainers (BD cat. no. 367861) for plasma samples, two 2.5-ml PAXgene tubes (BD cat. no. 762165) for RNA samples and two 4-ml Vacutainer® CPT™ Cell Preparation Tube (BD cat. no. 362781) for PBMC samples at scheduled visits:

- At the day 1 visit (baseline - randomization), blood samples will be collected prior to first IV RNS60/placebo dose (pre-dose, off drug blood sample).
- At the week 4, 12 and 24 study visits, the blood sample will be collected just prior to drug administration.
- An additional blood sample will be obtained at the week 48 visit (last study visit).

[figure not shown]

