11.3 Compliance

The compliance with the assigned at-home treatment will be measured by counting the number of used/unused syringes returned by the patient at each visit. A subject will be considered non-compliant if the amount of unused drug exceeds 25% of the assigned drug. The intake of less than 50% of the total amount of nebulized drug for 3 consecutive visits or in the event that the infusion is not performed for 2 consecutive visits implies withdrawal from the study.

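### As printed, 11.3 withdraws subjects after two missed weekly infusions without exempting the dosing changes 6.12 allows, and 6.10 ends endpoint collection when study drug stops

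*Combined protocol and SAP*

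**What the plan says.** Section 6.12 allows dose reduction or discontinuation for adverse events or other reasons, and lets a subject be kept on a reduced dose. It adds: "The option to continue with administration by IV only or inhalation only is allowable". No time limit is given. The reasons for and dates of any "suspension or dose reduction must be documented".

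Section 11.3 first covers home dosing: "The compliance with the assigned at-home treatment will be measured by counting the number of used/unused syringes". It then gives two triggers for leaving the study. One concerns low nebulized intake. The other concerns the weekly infusion: "in the event that the infusion is not performed for 2 consecutive visits implies withdrawal from the study". That clause states no reason, no exception and no reference to 6.12.

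The mandatory withdrawal list in 6.11 does not contain the two-infusion rule. Its dosing item is framed as repeated non-compliance: "intake of 50% of recommended dose or less in three consecutive intervals between visits". Its item on intolerable adverse events applies, "if deemed drug-related, non remitting with down titration".

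On what follows, 6.10 says: "Subjects who discontinue the study drug should be considered withdrawn from the study after the final visit assessments are performed". Table 2 has a single end-of-study column for drop-outs. Section 6.11 says that withdrawn subjects are not replaced. Section 11.2 keeps everyone who took at least one dose in the modified intention-to-treat set.

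**The concern.** Two matters are linked. The first is local. A site working from 6.11 and 6.12 would keep an inhalation-only subject, and a site working from 11.3 would withdraw the same subject. A two-week suspension of infusions, which 6.12 also foresees, meets the same trigger. The visible text does not say which section governs.

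The second reaches further. Leaving treatment and leaving the study are treated as one event, so anyone who stops drug early, for whatever reason, gives one more visit and then no scheduled endpoint data. These subjects still count in the main analysis set. The death-or-tracheostomy endpoint in 2.4 covers the whole study including follow-up, yet the visible text schedules no survival follow-up for them. The data could still be collected from willing subjects. The plan's likelihood analysis is valid, as 11.2 itself says, only if missingness depends on data already observed, so avoidable gaps put weight on that condition. The visible text also does not say how a drop-out sample taken between scheduled weeks enters a model with fixed observation times and an unstructured covariance. That gap applies to every drop-out.

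**Working it through.** **When the trigger is met.** Infusions are weekly (6.1). The infusion row of Table 2 covers day 1 and weeks 1 to 23, that is 1 + 23 = 24. Two missed infusions are 2/24 = 8.3% of the course and fall within 14 days of the last one given. Section 5.1 says "At the week 4, 12 and 24 study visits, the blood sample will be collected just prior to drug administration", which implies an infusion at week 24 as well; the fraction would then be 2/25 = 8.0%.

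**What is lost per subject.** Biomarkers are scheduled at weeks 0, 4, 12, 24 and 48, and the first four form the primary window. ALSFRS-R and FVC are scheduled at weeks 0, 4, 12, 24, 36 and 48 (screening not counted).

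| Last infusion | Trigger met | Primary-window biomarkers lost | Later biomarker lost | ALSFRS-R and FVC lost |
|---|---|---|---|---|
| Week 4 | Week 6 | 2 of 4 (weeks 12, 24) | Week 48 | 4 of 6 (weeks 12, 24, 36, 48) |
| Week 12 | Week 14 | 1 of 4 (week 24) | Week 48 | 3 of 6 (weeks 24, 36, 48) |

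Against this there is one drop-out visit, which includes all three measures.

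**The plan's own figure.** For T-reg, section 11.1 gives a difference of 0.25, SD 0.5 and a total of 128. A two-sample t-test at two-sided 0.05 with 80% power needs 63.8 per arm, so 64 per arm and 128 in total. The drop-out figure also agrees: 1 − (1 − 0.0175)^6 = 10.05%. With 142 enrolled, 142 × 0.90 = 127.8 are evaluable and power is 80.1%.

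**Effect of extra withdrawals on T-reg.** The documents give no rate of route change or suspension, so 2%, 5% and 10% are assumptions, taken as additional to the planned 10%. Each such subject is treated as having no week-24 value. Evaluable N = 142 × (0.90 − r), and the noncentrality is 0.5 × √(n/2) with n per arm.

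| Extra rate r | Evaluable N | Noncentrality | Power |
|---|---|---|---|
| 0 | 127.8 | 2.826 | 80.1% |
| 2% | 125.0 | 2.795 | 79.2% |
| 5% | 120.7 | 2.747 | 77.8% |
| 10% | 113.6 | 2.665 | 75.2% |

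The loss is 0.9 to 4.9 points. At these rates it is an upper bound, because the planned maximum likelihood analysis uses the earlier samples of these subjects and this calculation does not.

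**ALSFRS-R slope.** Inputs are the variance parameters in 11.1: intercept 31.8, slope 0.6687, covariance 0.8527, error 2.7, with time assumed to be in months. Further assumptions are a common baseline, visits at weeks 0, 4, 12 and 24, 71 per arm, and 10% ordinary drop-out after week 12. The slope difference giving 80% power is about 0.43 per month. If a further 2%, 5% or 10% of subjects are seen only at weeks 0, 4 and 7 (the drop-out visit), power is about 79.4%, 78.6% and 77.1%. If the week-7 visit cannot be used, it is 79.3%, 78.2% and 76.3%.

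**The case against.** A reader might infer that 6.12 and 11.3 flatly contradict each other. The documents do not support that. The infusion clause sits under a heading on compliance, directly after the definition of a non-compliant subject. Section 6.11 frames its dosing item as non-compliance and expects down-titration to be tried before withdrawal for a drug-related event. A documented change approved by the investigator can fairly be read as outside the rule. Section 6.14 on treatment compliance and sections 7.1 to 7.8, which cover infusion visits and the drop-out visit, are not in the public text and may say so. What stands is that the printed clause has no exception and no cross-reference.

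A reader might also infer that IV-only subjects are caught in the same way by the nebulized-intake rule. That is weaker: home compliance is measured on assigned drug, and a subject assigned no syringes can be read as falling outside it. The slightly different 50% dose thresholds in 6.11 and 11.3 are editorial and carry no weight here.

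On size, this is an exploratory pilot, tolerability to date was good, and the number affected could be zero. If the planned 10% drop-out already allows for protocol-required withdrawals, the power losses above are partly or wholly counted twice. All of this stands, and it rules out treating power as the main ground.

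It is tempting to conclude that the primary result would be biased. That is not shown. Bias would need withdrawals to depend on outcomes that the earlier data do not capture, and nothing in the documents establishes this.

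Finally, the 6.10 rule is a study-wide design choice, separate from the 11.3 wording. That is correct. It is raised here because it determines what a withdrawal costs, and it applies to every subject who stops drug early.

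**Conclusion.** The point holds as a wording gap with a broader, inexpensive improvement attached. Followed as printed, 11.3 would remove subjects whom 6.12 allows to continue, and 6.10 would end endpoint collection in subjects who may be willing to go on being assessed and who remain in the modified intention-to-treat set. The cost per subject is clear from Table 2: up to half of the primary-window biomarker samples for a stop after week 4, and more for an earlier stop. The trial-level cost is not known. Under assumed extra rates of 2% to 10% the power loss is small, at most about 1 to 5 points for T-reg and about 1 to 3 for the ALSFRS-R slope when the drop-out visit is usable. The case rests on data given up needlessly and on possible inconsistency between sites. Confidence in the 11.3 part is moderate, since text not in the public version may resolve it.

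**What to change.** 1. In 11.3 and 6.11, state that a documented, investigator-approved route change, dose reduction or suspension under 6.12 is not non-compliance and does not trigger withdrawal. If 6.14 or section 7 already says this, a cross-reference in 11.3 is enough.

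2. Amend 6.10, 6.11 and 11.3 so that stopping study drug ends treatment only. Unless consent is withdrawn, continue the remaining Table 2 assessments (biomarkers at weeks 4, 12, 24 and 48; ALSFRS-R and FVC at weeks 4, 12, 24, 36 and 48) and survival follow-up to week 48, and include these data in the modified intention-to-treat analysis. The 6.11 paragraph on stopping riluzole, which uses data only up to drug discontinuation, needs the same change. For subjects no longer infused, say that the biomarker sample is taken at the scheduled visit, since 5.1 times it by the dose.

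The first change is a sentence or two. The second changes follow-up for everyone who stops drug early, so it needs a protocol amendment and site instruction. Its running cost is some extra visits, already scheduled in Table 2, by subjects who are off drug or on reduced dosing.
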